1.1 How will you define adverse events (AE) for this study?

An adverse event will be considered any undesirable sign, symptom or medical or psychological condition **even if the event is not considered to be related** to the investigational drug/device/intervention. Medical condition/diseases present before starting the investigational drug/intervention will be considered adverse events only if they worsen after starting study treatment/intervention. An adverse event is also any undesirable and unintended effect of research occurring in human subjects as a result of the collection of identifiable private information under the research. Adverse events also include any problems associated with the use of an investigational device that adversely affects the rights, safety or welfare of subjects.

1.2 How will you define serious adverse events?

A serious adverse event will be considered any undesirable sign, symptom, or medical condition which is fatal, is life-threatening, requires or prolongs inpatient hospitalization, results in persistent or significant disability/incapacity, constitutes a congenital anomaly or birth defect, is medically significant and which the investigator regards as serious based on appropriate medical judgment. An important medical event is any AE that may not result in death, be life-threatening, or require hospitalization but may be considered an SAE when, based upon appropriate medical judgment, it may jeopardize the patient and may require medical or surgical intervention to prevent one of the outcomes listed in the definitions of SAEs.

1.3 What is the definition of an unanticipated problem?

Do not change this answer

An unanticipated problem is any event, experience that meets ALL 3 criteria below:

- Is unexpected in terms of nature, severity or frequency given the research procedures that are described in the protocol-related documents AND in the characteristics of the subject population being studied
- Related or possibly related to participation in research. This means that there is a reasonable possibility that the incident may have been caused by the procedures involved in the research study.
- The incident suggests that the research placed the subject or others at greater risk of harm than was previously known or recognized OR results in actual harm to the subject or others

1.4 What is the definition of a protocol violation?

Do not change this answer

A protocol violation is defined as any change, deviation, or departure from the study design or procedures of a research project that is NOT approved by the IRB-HSR prior to its initiation or implementation, OR deviation from standard operating procedures, Good Clinical Practices

(GCPs), federal, state or local regulations. Protocol violations may or may not be under the control of the study team or UVa staff. These protocol violations may be major or minor violations.

Additional Information: see the IRB-HSR website at

http://www.virginia.edu/vpr/irb/HSR_docs/Forms/Protocol_Violations_%20Enrollment_Exceptions_Instructions.doc

1.5 If pregnancy occurs how will this information be managed?

Adverse Event- will follow adverse event recording and reporting procedures outlined in section 3.

1.6 What is the definition of a Protocol Enrollment Exception?

NA- No outside sponsor

1.7 What is the definition of a data breach?

Do not change this answer

A data breach is defined in the HITECH Act (43 USC 17932) as an unauthorized acquisition, access, or use of protected health information (PHI) that compromises the security or privacy of such information.

Additional Information may be found on the IRB-HSR Website: [Data Breach](#)

2. Identified risks and plans to minimize risk

2.1 What risks are expected due to the intervention in this protocol?

Expected Risks related to study participation.	Frequency
Expected Risks related to study participation- volume of blood drawn	

 Significant anemia related to frequent blood sampling (hematocrit < 30%) 	 Occurs frequently  Occurs infrequently  Occurs rarely  Frequency unknown, but likely to be very rare

 Mild anemia (hematocrit < 36%) related to frequent blood sampling 	 Occurs frequently  Occurs infrequently  Occurs rarely  Frequency unknown
Expected Risks related to study participation- micronized progesterone	
GI upset (nausea, abdominal bloating, diarrhea)	 Occurs frequently  Occurs infrequently  Occurs rarely

IRB-HSR#8588: Assessment of the sensitivity of the hypothalamic GnRH pulse generator to estradiol and progesterone inhibition in normal and hyperandrogenemic adolescent girls (JCM010)

	 Frequency unknown  Occurs frequently  Occurs infrequently  Occurs rarely  Frequency unknown
CNS effects (sleepiness, headache, dizziness, fatigue, emotional lability, irritability)	 Occurs frequently  Occurs infrequently  Occurs rarely  Frequency unknown
Risk associated with estradiol:	
GI upset (nausea, abdominal bloating, diarrhea)	 Occurs frequently  Occurs infrequently  Occurs rarely  Frequency unknown
Breast Tenderness	 Occurs frequently  Occurs infrequently  Occurs rarely  Frequency unknown
Deep vein thrombosis	 Occurs frequently  Occurs infrequently  Occurs rarely  Frequency unknown, however occurs very rarely with long-term estrogen use (as with oral contraceptive pills), so would expect to be exceedingly rare with the short term administration in this protocol
Violation of subject's privacy and confidentiality	Minimized due to the requirements of the privacy plan in this protocol

Risk associated with IV needle placement:

Expected Risks related to study participation- IV placement	Frequency

 Infection at needle site 	 Occurs frequently,  Occurs infrequently  Occurs rarely  Frequency unknown, but likely to be very rare

 Bleeding at needle site 	 Occurs frequently,  Occurs infrequently  Occurs rarely  Frequency unknown

 Blood clot at needle site 	 Occurs frequently,  Occurs infrequently  Occurs rarely  Frequency unknown

 Pain at needle site 	 Occurs frequently,  Occurs infrequently  Occurs rarely  Frequency unknown

 Bruise at needle site 	 Occurs frequently,  Occurs infrequently  Occurs rarely

	 Frequency unknown
--	--------------------------------------------

Risk associated with iron supplementation

Expected Risks related to study participation- iron supplementation	Frequency Please pick one frequency from each box below

 • nausea 	 Occurs frequently,  Occurs infrequently  Occurs rarely  Frequency unknown

 • constipation 	 Occurs frequently,  Occurs infrequently  Occurs rarely  Frequency unknown

 • dark or black stools 	 Occurs frequently,  Occurs infrequently  Occurs rarely  Frequency unknown

Risk associated with EMLA cream (topical lidocaine and prilocaine, used to alleviate pain): The risks of lidocaine and prilocaine in general may include (frequency not defined) hypotension, angioedema, shock, hyperpigmentation, erythema, itching, rash, burning, urticaria, burning, stinging, edema bronchospasm, and hypersensitivity reactions. However, in the case of topical lidocaine/prilocaine use, the non-dermatologic adverse events mentioned above would be extremely unlikely unless large amounts of topical lidocaine/prilocaine were used (allowing significant systemic absorption).

Risk regarding wrist actigraphy: There are no known risks associated with the use of wrist actigraphy.

Risk of not being able to take hormonal medications: The risk of not taking hormonal medications is pregnancy.

2.2 List by bullet format a summary of safety tests/procedures/observations to be performed.

- Sterile technique will be used.
- Before participation in the study, all participants will be required to have a normal hemoglobin (≥ 11.0 g/dl for African American subjects and ≥ 11.5 g/dL for non-African American subjects). Hemoglobin levels will be measured prior to every admission, and the admission will only continue if the hemoglobin level is ≥ 11.0 g/dL for African American subjects or ≥ 11.5 g/dL for non-African American subjects.
- Blood loss will be carefully recorded and limited to a maximum of 7cc/kg (10% of estimated total blood volume) in 8 weeks. A total of 216.5 ml of blood will be drawn during the study (including estimated waste from frequent blood draws). Therefore, girls weighing less than 31 kg will not be able to participate. Iron supplementation (325 mg once or twice a day dependent on weight) will be prescribed to all participants.
- Topical lidocaine and prilocaine (EMLA) cream may be used to lessen pain associated with IV needle insertion.
- We will warn participants against becoming pregnant during the study. We will ask that the patient use a barrier method of birth control as needed during the study. Prior to each admission, β -hCG levels will be measured; if the β -hCG is positive, the study will be discontinued.

2.3 Under what criteria would an INDIVIDUAL SUBJECT’S study treatment or study participation be stopped or modified

At subject, PI or sponsor’s request

Treatment would be stopped if the subject had a serious adverse event deemed related to study

The study would be stopped in the patient has a positive pregnancy test or a hematocrit <36 and hemoglobin <12 prior to any of the 2 admissions.

2.4 Under what criteria would THE ENTIRE STUDY need to be stopped.

Per IRB, PI, DSMB, or sponsor discretion

Other: If there are an excessive number of unexpected adverse events that significantly alter the risk/benefit ratio for the study, the study will be terminated. All adverse events will be evaluated both individually and cumulatively by the study team and principal investigator as they arise, allowing for timely decisions regarding study continuation/termination.

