- Hemoglobin <11.5 g/dL for non-African American subjects; Hemoglobin < 11.0 g/dL for African American subjects (Subjects will be offered the opportunity to take iron supplementation for 60 days if their hemoglobin is below the above stated guidelines, and will then return for retesting of their hemoglobin. If still below the guidelines, they will be excluded.
- Weight < 31 kg
- History of peanut allergy, deep venous thrombosis, breast cancer, endometrial cancer, or cervical cancer
- On hormonal medications (including oral contraceptive pills) or on medications known to affect the reproductive axis within 3 months of the study

IRB-HSR#8588: Assessment of the sensitivity of the hypothalamic GnRH pulse generator to estradiol and progesterone inhibition in normal and hyperandrogenemic adolescent girls (JCM010)

- Pregnant or breastfeeding
- Participation in a research study within the past 30 days that involved taking a study drug.
- Participation in a research study that involved taking up to or greater than 473 ml's of blood within the past 60 days.
- Cigarette smoking
- History of surgery that required bedrest within the past 30 days
- Family history of hypercoagulability or unexplained thromboembolic disease (not in setting of bedrest, surgery, or malignancy)

3. List any restrictions on use of other drugs or treatments.

Subjects must discontinue all hormonally-active medications at least 3 months prior to the frequent sampling study (and 2 months prior to screening visit) and must not take any other medications known to affect the reproductive axis during the study. There are no dietary requirements for this study.

Study Design: Biomedical

1. Will controls be used?

Yes. Controls (normal healthy volunteers) will be used included in all analyses. Thus far, 28 controls have completed the study. Since this is adequate for our purposes, no additional controls will be enrolled. For the remainder of the study, only girls with hyperandrogenemia will be studies.

► IF YES, explain the kind of controls to be used.

Normal-weight, healthy adolescent girls.

2. What is the study design?

Biomedical

3. Is randomization involved?

No.

4. Does the study involve a placebo?

No.

Recruitment

1. Do you confirm that you are aware of the following?

Yes.

- *Finders fees paid to an individual are not allowed by UVa Policy*

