- *Only those members of the study team with a DEA# (license to prescribe drugs) are allowed to determine if a potential subject may be asked/informed to stop taking a drug which is an exclusion criteria.*
- *It is recommended that the potential subject notify their health care provider if they plan to stop a prescription drug.*

6. Will the study procedures be started the same day the subject is recruited for the study?

No.

7. How will the consenting process take place?

An outpatient screening visit is scheduled for volunteers who preliminarily qualify for the study. Copies of the approved consent and assent forms are sent to potential subjects beforehand, and we request that the volunteer and her parents review and discuss the forms prior to the screening visit. The screening visit is held in an outpatient screening room in the CRU or alternate UVA clinical unit. This allows for a private conversation between the study physician, the potential participant, and at least one of her parents (other individuals such as family members are allowed in the room if desired by the potential participant). The screening visit usually occurs in the morning, although rarely it will occur in

the afternoon. The aims, procedures, and potential risks of the study are first explained by the study physician. Importantly, the potential participant and her parents (if under 18) are given an opportunity to ask any questions, and concerns are addressed. In cases where the potential participant wants to begin the study and her parents concur, the participant, parents, and physician sign the consent form. In cases where only one parent is able to come to the screening visit, we allow the second parent to sign the form in advance of the visit. This is done in conjunction with a conversation during which we offer that parent an opportunity to ask any questions and confirm that they understand the study and are willing for their daughter to participate. We routinely inform potential participants verbally that signing the consent form does not compel them to continue participation in the study. The remainder of the outpatient screening visit (i.e., history, physical, screening blood tests) occurs immediately thereafter. Participants generally begin the main part of the study within 1-2 months of the screening visit.

8. Do you need to perform a “dry run” of any procedure outlined in this protocol? No.

Biomedical Research

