NOTICE: Investigators who are Members of the Clinical Staff at the University of Virginia Medical Center must have been granted clinical privileges to perform specific clinical privileges whether those procedures are experimental or standard. The IRB cannot grant clinical privileges. Performing procedures which are outside the scope of the clinical privileges that have been granted may result in denial of insurance coverage should claims of negligence or malpractice arise. Contact the Clinical Staff Office- [name] for further information.

1. What will be done in this protocol?

All procedures performed in this protocol are being done solely to answer a research question and generate generalizable knowledge.

Outpatient Screening

After a potential subject is identified, we will arrange for her to come to the CRU or alternate UVA clinical unit for an outpatient screening exam. The goals and procedures of the study will be explained to the potential subject and her parents (if applicable), and they will be given the opportunity to ask any questions. The potential subject and her parents (if applicable) will be asked to sign the assent and consent forms.

- A physician will record a family and personal medical history and perform a physical exam.
- Subjects will need to fast for a minimum of 8 hours prior to screening blood draw.
- Blood will be drawn for screening tests (CBC, Chem 17 including LFTs, prolactin, LH, FSH, E₁, E₂, P, total T, androstenedione, 17-OHP, DHEA-S, fasting insulin, glucose, TSH, hCG, cholesterol, LDL and HDL).
- Patients with elevated 17-OHP on screening will be referred to their pediatricians for further testing to rule out congenital adrenal hyperplasia. They will only be able to continue with the study if they have documented normal 17-OHP levels following a cosyntropin stimulation test
- Potential subjects must fall within the normal range on all blood tests to be admitted to the study, except for hyperandrogenemic girls who will be expected to have some abnormal hormone levels.
- In addition, if the subject's hemoglobin is less than 11.0 for African American subjects or < 11.5 for non-African American subjects at the time of screening, we will offer the option of taking

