oral iron supplementation at a dose of 1-2 mg/kg for 60 days. Subjects weighing ≤ 36 kg will be given 300-325 mg oral ferrous gluconate daily (containing 36 mg of elemental iron); subjects weighing >36 kg will be given 300-325 mg oral ferrous gluconate twice daily. Following the course of iron supplementation, the subject will then return to the CRU or clinical unit for a repeat hematocrit and hemoglobin, and will only be able to proceed with the study if her hemoglobin is greater than or equal to 11.5 g/dL for non-African American subjects or greater than or equal to 11.0 g/dL for African American subjects.

- If the screening tests show that the subject is eligible for the study, she will be given oral iron supplementation at a dose of 1-2 mg/kg for 30 days to help prevent anemia during and after the study. Subjects weighing ≤ 36 kg will be given 300-325 mg oral ferrous gluconate daily (containing 36 mg of elemental iron); subjects weighing >36 kg will be given 300-325 mg oral ferrous gluconate twice daily. The admission can take place any time during or after the iron supplementation.

Day 0: First inpatient admission

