The subject will be admitted to the CRU, alternate UVA hospital unit, or off-site hotel at 1700 hr, when a hemoglobin test will be done. In order to continue with the admission, girls must have a hemoglobin of at least 11.0 g/dL for African American subjects or at least 11.5 g/dL for non-African American subjects. In general, parents are welcome to stay with their child at the off-site hotel if they wish. If the overnight portion of the study is to be done at an off-site hotel, the subject may stay without a parent or legal guardian, as long as two CRU staff are present. Whether or not a parent needs to remain during the overnight admission will be discussed when the visit is scheduled. . If the overnight portion of the study is to be done at a hotel, the hemoglobin check will be done at the CRU 1-5 days prior to the overnight admission. Alternatively, subjects may come to the CRU early on the day of their admission before their scheduled admission time. The study team will be responsible for scheduling this with the subject. A urine pregnancy test will be done. The pregnancy test must be negative for continued participation. A small amount of topical lidocaine/prilocaine cream (EMLA cream) may be applied to facilitate IV line placement. An IV line will be placed in a forearm vein and blood draws will begin at 1900 hr. Samples will be taken every 10 minutes. Most samples will be 0.75 mL, used to analyze levels of FSH and LH. 2.5 mL samples will be taken every 2 hours to analyze levels of estradiol, progesterone, testosterone, cortisol and DHEA. An additional 3.0 mL sample will be analyzed for fasting insulin, Insulin-like Growth Factor 1 (IGF-1), fasting glucose, estrone, sex hormone binding globulin, DHEA-S, androstenedione and a number of cytokines and adipokines, including adiponectin, leptin, resistin, PAI-1, IL-1b, IL-6, IL-8, TNFa, MCP-1, HGF and NGF. (Due to new technologies adipokines and cytokines can be measured in a total of 25 ul of serum, thereby allowing us to measure these without substantially increasing the necessary blood volume).

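### Section 2.3 stops a girl at hematocrit <36 with hemoglobin <12, but the admission checks test hemoglobin alone at 11.0 or 11.5 g/dL; no text says how the two rules combine, and no pre-admission check names a hematocrit

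*Combined protocol and SAP*

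**What the plan says.** Section 2.3 of the Data and Safety Monitoring Plan stops the study for a girl with a positive pregnancy test or "a hematocrit <36 and hemoglobin <12 prior to any of the 2 admissions". The two blood conditions are joined, so both must hold, and the limits are the same for every girl.

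The other places use hemoglobin alone, with limits that differ by race:

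- **Exclusion criteria:** "Hemoglobin <11.5 g/dL for non-African American subjects; Hemoglobin < 11.0 g/dL for African American subjects".
- **Outpatient Screening:** iron is offered when "hemoglobin is less than 11.0 for African American subjects or < 11.5 for non-African American subjects at the time of screening". After 60 days of iron, "the subject will then return to the CRU or clinical unit for a repeat hematocrit and hemoglobin". She "will only be able to proceed with the study if her hemoglobin is greater than or equal to 11.5 g/dL for non-African American subjects" (11.0 g/dL for African American girls). Hematocrit is measured here, but the stated condition for going on rests on hemoglobin.
- **Day 0, first admission:** the girl arrives at 1700 hr, "when a hemoglobin test will be done", and to continue "girls must have a hemoglobin of at least 11.0 g/dL for African American subjects or at least 11.5 g/dL for non-African American subjects". If the night is spent at a hotel, the hemoglobin check is made at the CRU 1 to 5 days before, or earlier on the day of admission.
- **Day 7, second admission:** the first admission's procedure is repeated.
- **Section 2.2:** hemoglobin is measured before every admission against the same two limits, which the section calls normal.

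Section 2.1 lists mild anemia, defined by hematocrit below 36%, as a rare expected risk of the sampling. None of these texts says how the section 2.3 stop relates to the hemoglobin limits.

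**The concern.** Sections 2.2 and 2.3 are adjacent parts of one safety plan and bear on the same moment, the check before each overnight admission. They use different variables and different cut-offs. A nurse or physician who runs the check described under Day 0 and in section 2.2 gets a hemoglobin, compares it with 11.0 or 11.5 g/dL, and continues. Section 2.3 would stop some of the same girls, and it depends on a value that the described check does not include.

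What is at stake is consistent handling of a safety decision in children who undergo two nights of sampling every 10 minutes. There is also a link to the data. The primary outcome is the fall in LH pulse frequency after one week of treatment, so a girl stopped before the second admission has no primary outcome value.

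**Working it through.** The plan states no figure to reproduce, so the check sets the two rules side by side. Section 2.3 prints no units; I take them to be % and g/dL, as elsewhere in the protocol.

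**Rules**

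- Admission check (Day 0, Day 7 by reference, section 2.2): continue only if hemoglobin is at least L, with L = 11.0 (African American) or 11.5 (non-African American).
- Section 2.3: stop if hematocrit <36 *and* hemoglobin <12.

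**All combinations**

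- Hemoglobin 12.0 or above: the check is met, and 2.3 cannot be met whatever the hematocrit. No conflict.
- Hemoglobin from L to <12.0, hematocrit 36 or above: the check is met and 2.3 is not. No conflict.
- Hemoglobin from L to <12.0, hematocrit <36: the check is met **and** the 2.3 stop is met.
- Hemoglobin below L, hematocrit <36: the admission ends and 2.3 is met. No conflict.
- Hemoglobin below L, hematocrit 36 or above: the admission ends but 2.3 is not met. The admission decision is clear; section 2.3 does not call for ending participation.

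**Width of the overlap, given hematocrit <36**

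- African American: 12.0 − 11.0 = 1.0 g/dL.
- Non-African American: 12.0 − 11.5 = 0.5 g/dL.

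Trying hemoglobin values from 10.9 to 12.0 with hematocrit 35 and 36 gives the same regions. For example, at hemoglobin 11.7 and hematocrit 35, both groups pass the admission check and meet the stop.

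**Where a hematocrit could come from**

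- The screening CBC. Under Recruitment, item 7: "Participants generally begin the main part of the study within 1-2 months of the screening visit".
- The repeat test after iron, which is done only for girls whose hemoglobin was low at screening.

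Both come before the first admission's sampling. A screening value is at least prior to the first admission, as section 2.3 requires. For the second admission, neither can show what the first night's sampling did to hematocrit, and section 2.1 names that effect as an expected, if rare, risk. No later hematocrit is named.

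**The case against.** The strongest reply is that the rules do not contradict each other. The hemoglobin limits are necessary conditions: the admission continues *only if* they are met, which does not promise that it will continue. Section 2.3 can then be a further safeguard on top, and the risk table's definition of mild anemia at hematocrit below 36% fits that reading. A site that applies every section would stop the girl in the overlap. This stands, and a reader who infers a flat logical contradiction goes further than the text. What remains is that no passage says the rules are cumulative. The text on re-testing after iron measures hematocrit and still states its condition on hemoglobin alone.

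A reader might also infer that section 2.3 cannot be applied at all because hematocrit is not measured. The documents do not support that either. They do not say whether a hematocrit is reported with the pre-admission hemoglobin, and section 2.3 itself implies that one is available. What can be said is that no passage names a hematocrit at either pre-admission check.

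Finally, the rules trigger different actions: one ends an admission, the other ends participation. That is a fair distinction, and it is a further reason to state how they connect.

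**Conclusion.** The point holds as a minor inconsistency in a safety rule. With hematocrit below 36, a girl at hemoglobin 11.0 to <12.0 g/dL (African American) or 11.5 to <12.0 g/dL (non-African American) passes the described check and meets the section 2.3 stop. Staff who run only the named check would continue an admission that section 2.3 says to stop. The conclusion rests on the wording alone, plus the assumption about units.

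The number of girls in the overlap cannot be computed, because the documents give no distribution of hemoglobin or hematocrit. A reader might connect this rule with the 35% historical dropout and withdrawal rate, or suspect that it tilts the comparison between groups. The documents support neither: they give no reasons for withdrawal and report no girl stopped on this ground.

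**What to change.** - **Reconcile the text.** Align the exclusion criteria, Outpatient Screening, the Day 0 and Day 7 procedures, and sections 2.2 and 2.3, so that either one consistent rule governs both admissions or two rules are stated to apply together. Say whether failing each one ends the admission or ends participation.
- **Name the tests.** At each pre-admission check, list every value the rule needs. If hematocrit stays, establish whether it can be read from the sample already drawn for hemoglobin; the documents do not say. Any extra blood must fit the limit of 7 cc/kg in 8 weeks given in section 2.2. At the minimum weight that is 7 × 31 = 217 ml against 216.5 ml planned, or 0.5 ml to spare if all of it falls within one 8-week window (an assumption).
- **Check the records.** Look for girls stopped under section 2.3 and for girls admitted with hemoglobin inside the overlap, and note which rule was applied and whether a hematocrit was available.

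The cost is a short wording amendment and a review of existing records; the protocol counts 62 girls as having completed so far, plus those who withdrew. Which thresholds apply, and whether hematocrit belongs in the rule, is for the study team to decide.
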